**D. Executive Summary**

Pre-eclampsia and eclampsia pose a significant threat to the health of mothers globally. The WHO estimates that 50,000 women worldwide die annually as a result of pre-eclampsia or eclampsia [1], with the majority in developing countries. The research team at Rice University has developed Sphygmo, an automatic blood pressure monitor to be used for the monitoring and diagnosis of pre-eclampsia in pregnant women, particularly in low-resource settings where current blood pressure monitoring is limited. This study aims to evaluate the clinical monitoring and diagnostic capabilities of the device in the setting for which it was designed - a low-resource hospital.

This is a **3- phase clinical community trial**. The first two phases are being completed by Rice University in Houston Texas. In phase 1, we will test the blood pressure monitor on healthy women followed by a secondary phase to test the monitor on pregnant women. Phase 3, in Malawi, the study will compare the Sphygmo device to a commercially available automatic blood pressure monitor that has been previously validated for accuracy in pre-eclamptic women and clinical auscultatory measurements taken by observers using a stethoscope and aneroid gauge [2, 3]. The main objective of this study is to determine whether the Sphygmo device correctly identifies instances where systolic and diastolic blood pressures meet the diagnostic criteria for mild or severe pre-eclampsia during monitoring of at-risk mothers.

Additionally, this study aims to understand the occurrence and type of any complications associated with the usability and function of Sphygmo in a resource-limited clinical setting.

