The study will include 20 eligible and consenting women at QECH who are clinically identified as at-risk for pre-eclampsia or have already been diagnosed with pre-eclampsia. All participants will undergo the same protocol (monitoring with Sphygmo, the commercially available device, and using the auscultatory method). First, a nurse will fit a Sphygmo device cuff on one arm of the subject and the commercial cuff on the opposite arm. The nurse will program identical alarm thresholds and measurement intervals on the new device. A trained research assistant will be continuously on hand to assist the nurse in the device setup and record the blood pressure measurements and any alarm indications made by each device. Blood pressure measurements by Sphygmo and the commercial device will continue until monitoring is no longer clinically prescribed. All clinical decisions will be made according to the commercial device measurements. In addition, every hour an observer will take a blood pressure reading using the clinical auscultatory method to confirm that the readings of both the commercial device and Sphygmo are accurate.

The key results of the study will be the sensitivity and specificity of the Sphygmo device for identifying blood pressure levels corresponding to mild and severe pre-eclampsia. Additionally, a complication rate will be determined in regards to any user errors or device malfunction. These results will provide information on the performance, use, and usability of the device in its intended setting; this information will also alert the research team of any necessary design modifications for the device. The results of the study will be submitted for publication in a relevant research journal, such as the *American Journal of Obstetrics and Gynecology*.

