## vi. Data Collection

Data will be collected on paper forms (Appendix 2) as is consistent with current clinical practice. Clinical and/or research personnel will record information, excluding personal identifiers, on a standardized patient monitoring form. After the patient's participation is completed, the research coordinator will collect and scan the form.

The following data points will be collected/processed:

- Patient history variables:
  - *Age*
  - *Gravidity*
  - *Estimated gestational age (or hours since delivery)*
  - *Mode of admission to hospital*
  - *Number of previous antenatal care visits*
- Threshold Accuracy:
  - *True positive (TP): Control device and Sphygmo cross alarm threshold*
  - *True negative (TN): Control device and Sphygmo do not cross alarm threshold*
  - *False positive (FP): Control device does not cross alarm threshold but Sphygmo does*
  - *False negative (FN): Control device crosses alarm threshold but Sphygmo does not*
  - *Sensitivity: TP/(TP+FN) with confidence intervals*
  - *Specificity: TN/(TN+FP) with confidence intervals*
- Usability:
  - *User error: dichotomous variable indicating incidence of nurse error (max 1 per device interaction)*
  - *Total number of Sphygmo device interactions by nurse*
  - *Percent of error-free device interactions by nurses*
- Device Function:
  - *Device malfunction: dichotomous variable indicating incidence of device malfunction (max 1 per device use)*
  - *Total number of device uses*
  - *Percent of malfunction-free device uses*

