## Blood Pressure Measurements

Measurement #	Time	Control Systolic / Diastolic (mmHg)	Test Device Systolic / Diastolic (mmHg)
1			
2			
3			
4			
5			
6			
7			
8			
9			
10			
11			
12			
13			
14			
15			
16			
17			
18			
19			
20			
21			
22			
23			
24			
25			
26			
27			
28			
29			
30			
31			
32			
33			
34			
35			
36			
37			
38			
39			
40			
41			
42			
43			
44			
45			

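### The hourly auscultatory check on both monitors is not protected from the observer already knowing the monitors' values, and its result has no place on the form

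*Combined protocol and SAP*

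**What the plan says.** Section D describes three methods used on every woman: Sphygmo, a commercial monitor, and "clinical auscultatory measurements taken by observers using a stethoscope and aneroid gauge". Section H.iii (Study Population) repeats the three.

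The purpose of the third method is given once, in section D: "every hour an observer will take a blood pressure reading using the clinical auscultatory method to confirm that the readings". The sentence goes on to name the two automatic monitors, whose accuracy is what the reading is meant to confirm.

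The same paragraph describes the setting. The two automatic devices run together, one on each arm: "First, a nurse will fit a Sphygmo device cuff on one arm of the subject and the commercial cuff on the opposite arm". Their output is logged by staff at the bedside: "A trained research assistant will be continuously on hand to assist the nurse in the device setup and record the blood pressure measurements", along with alarms. The Blood Pressure Measurements form has one column for the control and one headed "Test Device Systolic / Diastolic (mmHg)", side by side on each row. It has no column for auscultation.

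The accuracy outcomes in section H.vi compare the two devices only, for example "True positive (TP): Control device and Sphygmo cross alarm threshold".

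**The concern.** Of the three methods, only auscultation depends on a person judging the value, by matching sounds to a gauge. Such a reading tests the monitors only if it is free to disagree with them. Here the observer is asked to confirm two readings that may already be known, either from the displays, from the form, or from having just written them down.

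Auscultation is a named comparator and the only evidence gathered within the study on whether the commercial monitor is reading correctly on this ward. That monitor is the reference for every sensitivity and specificity count and guides all clinical decisions. If the check is influenced by what it is checking, agreement or disagreement with it means less than it appears to. Readings taken with knowledge of the displays cannot be repaired afterwards.

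**Working it through.** The plan gives no figure to reproduce here, so the check consists of reading the sections against each other, then one illustration of direction.

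**1. Is any safeguard stated?** Five would serve: masking of the observer, displays out of view, a fixed reading order, writing down before disclosure, or a separate person for each task. Each place where one would be expected was read.

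| Place | What it says about the auscultatory reading | Safeguard |
|---|---|---|
| D. Executive Summary | Hourly, by an observer, to confirm both devices | None |
| H.iii Study Population | One of three methods for all participants | None |
| H.vi Data Collection | Not mentioned | None |
| H.vii Data Management and Analysis | Not mentioned | None |
| Blood Pressure Measurements form | No column | None |

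**2. Who is the observer?** Section D mentions a nurse, a research assistant and an observer, but does not say that the observer is a different person from the other two. Section L budgets salaries for a study coordinator and a nurse only. The observer may therefore be the assistant who has just recorded both devices.

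**3. Which results use the reading?** Section H.vi defines sensitivity as TP/(TP+FN) and specificity as TN/(TN+FP). All four counts are set by whether the control and Sphygmo cross the alarm threshold. Auscultation enters none of them, so an influenced observer changes neither ratio.

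**4. Which way would the bias run?** Let a be the reading an uninfluenced observer would give, c the control value, s the Sphygmo value, and d the display that draws the observer. If the reading moves a fraction w toward d, then r = a + w(d − a). The values below are assumed, in mmHg, and serve only to show direction: a = 142, c = 150, s = 134, w = 0.5.

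- Without influence: c − a = 8 and s − a = −8.
- Drawn to the control: r = 142 + 0.5 × 8 = 146. Then c − r = 4 and s − r = −12. The control looks better and Sphygmo worse.
- Drawn to Sphygmo: r = 142 + 0.5 × (−8) = 138. Then c − r = 12 and s − r = −4. The reverse holds.

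If both displays erred in the same direction by the same amount, both differences would shrink. The direction therefore depends on which display is followed and on how the two devices differ, neither of which the documents give.

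**The case against.** The strongest objection is that no planned result depends on this reading. The outcomes in section H.vi and the analysis in section H.vii do not use it, the form does not hold it, and no agreement statistic is planned. The commercial monitor is described as already validated in pre-eclamptic women (section D) and FDA-approved (section I), so the reference does not rest on the hourly reading. The study is also a pilot meant to inform the size of a later trial (section H.v).

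Most of this stands, and it limits the point. A reader might infer that the sensitivity and specificity are themselves biased; their definitions rule that out as a direct effect. A reader might also infer that agreement is always overstated, or that the check could never expose an inaccurate device. With two displays, neither follows. Nor do the documents say that the observer does look at the screens; the bedside layout is not described. The point is only that nothing prevents it.

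The objection does not remove the concern. The plan names auscultation as a comparator and asks it to confirm both devices in this setting, despite the earlier validation. A check that the plan considers worth making every hour should be able to fail. That the value has no column and no analysis is a second gap in the same procedure, not a reason to leave the first.

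**Conclusion.** The concern holds in a limited form. As written, the procedure allows the hourly auscultatory reading to be influenced by the values it is meant to test, possibly because the same person records both. This weakens the comparison with auscultation and the only in-study check on the commercial monitor. It does not directly alter the planned sensitivity and specificity. No magnitude can be stated: the documents give nothing on how far an observer might be drawn, and the direction is not fixed.

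The conclusion assumes that no masking rule appears in the pages between the Appendix 1 heading and the data forms, which were not available for this check. The methods sections and the measurement form, where such a rule would belong, contain none. The change should be made before data collection because the readings cannot be masked later.

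**What to change.** Add to the procedure in section D that, each hour, the auscultatory systolic and diastolic are taken and written down before the observer looks at either device's current reading or at the paired form. Assign the task to whichever existing staff member, nurse or research assistant, did not record the most recent device values.

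Add an auscultatory systolic/diastolic column to the Blood Pressure Measurements form, so that the written value is transferred to the matching row and compared with both devices. Name that comparison in section H.vii, so that the column has a stated use.

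The monitors' displays and alarms stay in normal clinical use. Covering a screen is not needed, and would not mask someone who had just recorded its values.

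The cost is a sentence in the procedure, a column on the form, a line in the analysis plan and a small change in workflow each hour. No extra staff or participants are required. Masking will be incomplete whenever one person has to do both tasks; noting on the form when that happens would show how often.

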## **E. Background/Introduction**

Pre-eclampsia is characterized by hypertension and the presence of protein in urine of a pregnant woman and typically appears late in the pregnancy. Women with pre-eclampsia are at an elevated risk for stroke, organ dysfunction, blood clotting issues, pulmonary edema, and eclampsia [4]. Eclampsia is defined as the occurrence of seizures not attributed to other causes in women with pre-eclampsia [5].

The WHO estimates that 50,000 women worldwide die annually as a result of pre-eclampsia or eclampsia [1]. However, the vast majority of cases occur in developing countries where risk of dying from pre-eclampsia or eclampsia is 300 times higher than in the developed world [4].

One major obstacle to the reduction of maternal deaths from pre-eclampsia complications or eclampsia is the difficulty of diagnosis. While the diagnostic criteria for pre-eclampsia are clear in the literature [6, 7], early detection is unavailable in many clinical settings in the developing world. The diagnosis and monitoring of pre-eclampsia relies on measurements of blood pressure and proteinuria [8]. Unfortunately, the repeated use of mercury sphygmomanometry to monitor pre-eclampsia is too time-intensive for most resource-constrained clinical settings.

In the absence of regular measurements to observe the effects of treatment and the condition of the patient, a mother's safety may be compromised.

Further, automatic monitors appropriate for hospital use are prohibitively expensive for the low-resource settings where they are most needed. Standard commercial devices such as the Dinamap ProCare monitor (GE Healthcare) is the only known monitor with an accuracy for pre-eclamptic women that meets the standards of the British Hypertension Society (BHS) and is appropriate for hospital monitoring [2, 3]. Commercial hospital monitors are generally priced in the \$1000-\$2000 range.

#### **F. Justification**

Pregnancy-related hypertensive disorders cause 50,000 deaths annually, primarily in the developing world [1]. One major barrier to the diagnosis and management of pre-eclampsia is the time-intensive nature of conventional mercury sphygmomanometry, which is difficult in low-resource settings. There is a need for a blood pressure monitor that can independently monitor blood pressure and alarm if the pressure reaches the diagnostic criteria for mild or severe pre-eclampsia. This device must be shown to have a high level of accuracy and usability in low-resource settings.

#### **G. Objectives of the study**

##### Broad:

A team of engineers from Rice University has recently developed Sphygmo, an ambulatory blood pressure monitor which costs only \$50. This study aims to evaluate the ability of this device to monitor for the development of mild and severe pre-eclampsia in women in a resource-limited setting.

##### Specific:

- Primary Efficacy Objective: Determine whether the Sphygmo device correctly identifies instances where systolic and diastolic blood pressures meet the diagnostic criteria for mild or severe pre-eclampsia during monitoring of at-risk mothers.
- Primary Usability Objective: Understand the occurrence and type of any complications associated with the usability and function of Sphygmo in a resource-limited clinical setting.

#### **H. Research Methodology/Materials and Methods**

##### i. Study Type

This is a **3- phase clinical community trial**. The first two phases are being completed by Rice University in Houston Texas. In phase 1, we will test the blood pressure monitor on healthy women followed by a secondary phase to test the monitor on pregnant women. Phase 3, in

Malawi, the study will compare the Sphygmo device to a commercially available automatic blood pressure monitor on women who are at-risk for pre-eclampsia or have already been diagnosed with pre-eclampsia.

#### ii. Study Place

After two initial testing phases conducted in Houston, Texas, we will conduct the pilot study at Queen Elizabeth's Central Hospital in Blantyre, Malawi. Malawi represents an ideal location to conduct such a study as there are approximately 17,000 cases of pre-eclampsia annually.

#### iii. Study Population

The study will include 20 women in Malawi who are clinically identified as at-risk for pre-eclampsia or have already been diagnosed with pre-eclampsia. These women will either be pregnant or up to 48 hours postpartum. All participants in the study will undergo the same protocol (monitoring with Sphygmo, the commercial device, and using the auscultatory method). All eligible and consenting women will be enrolled in the study if a Sphygmo device and the commercial monitor are available at the time of clinical need for blood pressure monitoring.

#### iv. Study Period

We anticipate that the clinical assessment in Malawi will take 1-4months to complete.

#### v. Sample Size

The Malawi study is a pilot study that is designed to provide data to be able to calculate the number of patients that would be needed in a full clinical trial to evaluate the efficacy of Sphygmo in diagnosing pre-eclampsia. As such, a sample of 10 participants would indicate how large of a sample would be required for the subsequent clinical trial. The sample size of 10 was suggested by collaborating clinical partners and feedback from statisticians. However, due to some patients potentially choosing to end study participation, the study team (researchers and clinical partners) will require a sample size of 20 to ensure the appropriate amount of data is collected.

The inclusion criteria for the clinical study in Malawi:

- Women who have been identified as at-risk for pre-eclampsia or have been diagnosed with pre-eclampsia during a visit to QECH.
- Women who have been clinically identified to benefit from continuous blood pressure monitoring.
- Women ages 18 or older.

The exclusion criteria for the clinical study in Malawi are as follows:

- Pregnant women who have already developed eclampsia.
- Women under age 18.

## vi. Data Collection

Data will be collected on paper forms (Appendix 2) as is consistent with current clinical practice. Clinical and/or research personnel will record information, excluding personal identifiers, on a standardized patient monitoring form. After the patient's participation is completed, the research coordinator will collect and scan the form.

The following data points will be collected/processed:

- Patient history variables:
  - *Age*
  - *Gravidity*
  - *Estimated gestational age (or hours since delivery)*
  - *Mode of admission to hospital*
  - *Number of previous antenatal care visits*
- Threshold Accuracy:
  - *True positive (TP): Control device and Sphygmo cross alarm threshold*
  - *True negative (TN): Control device and Sphygmo do not cross alarm threshold*
  - *False positive (FP): Control device does not cross alarm threshold but Sphygmo does*
  - *False negative (FN): Control device crosses alarm threshold but Sphygmo does not*
  - *Sensitivity: TP/(TP+FN) with confidence intervals*
  - *Specificity: TN/(TN+FP) with confidence intervals*
- Usability:
  - *User error: dichotomous variable indicating incidence of nurse error (max 1 per device interaction)*
  - *Total number of Sphygmo device interactions by nurse*
  - *Percent of error-free device interactions by nurses*
- Device Function:
  - *Device malfunction: dichotomous variable indicating incidence of device malfunction (max 1 per device use)*
  - *Total number of device uses*
  - *Percent of malfunction-free device uses*

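### Sensitivity and specificity are scored against a fallible control, so they measure agreement with it; with independent errors even a perfect Sphygmo scores below 100%

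*Combined protocol and SAP*

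**What the plan says.** Section H.vi (Data Collection, Threshold Accuracy) has two discordant cells: "False negative (FN): Control device crosses alarm threshold but Sphygmo does not" and "False positive (FP): Control device does not cross alarm threshold but Sphygmo does". From these come "Sensitivity: TP/(TP+FN) with confidence intervals" and "Specificity: TN/(TN+FP) with confidence intervals". The control is the only reference, and there is no rule for settling a discordant result.

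The Executive Summary (section D) has a sentence that opens "The key results of the study will be the sensitivity and specificity of the Sphygmo device for identifying blood pressure levels corresponding to mild and" and then names the severe form as well. It also has an observer take an hourly auscultatory reading "to confirm that the readings of both the commercial device and Sphygmo are accurate". That reading does not enter the four definitions, and the form's Blood Pressure Measurements table has no column for it. The table holds one control value and one test-device value per measurement number. The two cuffs are on opposite arms.

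The analysis plan (H.vii) is descriptive: means, sensitivity and specificity, rates and proportions. It has no agreement analysis and no allowance for error in the reference. Section H.v says the pilot's data are meant to size a full trial.

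**The concern.** A single cuff reading has random error, whichever monitor takes it. When true pressure is near a cut-off, that error can put the two monitors on opposite sides even if Sphygmo is exact. H.vi charges all such cases to Sphygmo. The plan does not itself treat the control as error-free, since it schedules a check on it.

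The key results would therefore carry the name of accuracy while measuring agreement with another fallible monitor. A reader of the publication could take control error for missed severe pressures. The full trial could also be sized on a figure that is not Sphygmo's sensitivity.

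**Working it through.** **No plan figure to reproduce.** The documents state no expected sensitivity, specificity, device error or precision. The sample size (10, raised to 20) has no statistical inputs and does not bear on this point.

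**Inputs.** The scoring rule is from H.vi. Everything else is assumed, because the documents give no value: systolic cut-offs of 160 (severe type) and 140 (mild type), used for calculation only; normally distributed true pressure with mean m and SD s over readings; control error SD σ.

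**Model.** True pressure T ~ N(m, s²); control C = T + e_C; Sphygmo S = T + e_S. For cut-off c:
- reported sensitivity = P(S ≥ c and C ≥ c) / P(C ≥ c)
- reported specificity = P(S < c and C < c) / P(C < c)

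**Step 1: perfect Sphygmo (S = T), independent control error.** Worked case m = 145, s = 15, c = 160, σ = 6:
- SD of C = √(225 + 36) = 16.16; correlation of T and C = 15/16.16 = 0.93
- P(C ≥ 160) = 0.1766; P(T ≥ 160) = 0.1587; joint = 0.1291
- reported sensitivity = 0.1291/0.1766 = 73%
- reported specificity = (1 − 0.1587 − 0.1766 + 0.1291)/(1 − 0.1766) = 0.7938/0.8234 = 96%

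Same calculation at cut-off 160 for other assumptions:

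| Mean | SD | Control error SD | Sensitivity | Specificity |
|---|---|---|---|---|
| 145 | 15 | 4 | 82% | 97% |
| 145 | 15 | 5 | 78% | 97% |
| 145 | 15 | 6 | 73% | 96% |
| 145 | 15 | 8 | 65% | 96% |
| 150 | 20 | 4 | 91% | 96% |
| 155 | 25 | 4 | 94% | 96% |

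A wider grid (mean 135 to 150, SD 12 to 20) gives sensitivity of 71–93%, 51–88% and 31–81% for control error SD 3, 5 and 8. The low ends come from mean 135 and SD 12, where few readings are severe. At cut-off 140 the same grid gives sensitivity 89–97%, 82–95% and 72–93%, and specificity 85–96%, 75–94% and 62–91%.

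**Step 2: Sphygmo exactly as good as the control (both error SD 6, independent).** At m = 145, s = 15, c = 160:
- true sensitivity = 0.1291/0.1587 = 81%
- correlation of S and C = 225/261 = 0.86; joint = 0.1222; reported = 0.1222/0.1766 = 69%

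Mild-type case (mean 140, cut-off 140): true 88%, reported 83%.

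**Step 3: correlated errors.** With error correlation r, the correlation of S and C is (225 + 36r)/261. Severe-type case, true sensitivity 81%:
- r = 0.5: reported 78%
- r = 0.7: reported 83%
- r = 0.9: reported 90%

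The direction reverses between r = 0.5 and 0.7. Even with independent errors, reported sensitivity exceeded the true value when mean pressure was far above the cut-off and Sphygmo was noisy (mean 165, cut-off 140, Sphygmo error SD 8 or 12).

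**Step 4: would control against next control reading serve as a floor?** Split the true SD of 15 into between-woman 12 and within-woman 9 (144 + 81 = 225), with total error SD 6 for each device. An equally good Sphygmo with independent error scores 69%, as in step 2.
- If 4 mmHg of the control's error SD persists within a woman and true pressure has lag correlation 0.95, consecutive control readings correlate at (144 + 0.95×81 + 16)/261 = 0.91. They agree with each other 75% of the time among positives, above 69%.
- With no persistent error and lag correlation 0.5, the correlation is (144 + 0.5×81)/261 = 0.71 and the agreement is 55%, below 69%.

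So it can fall on either side.

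**The case against.** The strongest reply has four parts.

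- **The reference is disclosed.** H.vi names a control device, the study is a descriptive pilot with no pass mark, and the paired pressures are on the form for later examination. This limits the stakes. It does not answer the point, because the Executive Summary still presents the result as Sphygmo's ability to identify mild and severe levels, and H.v uses the data to plan a full trial.
- **The size is assumed.** This stands. A reader might infer that a ceiling well below 100% has been shown. It has not: a wide pressure spread and a small control error give 91% or 94%. Section E says a commercial monitor meets a validation standard in pre-eclamptic women, which does not favour the larger error SDs, though no figure is given and meeting a standard does not make one reading exact.
- **The direction is conditional.** This stands too. A reader might infer that control error always counts against Sphygmo. That holds for a perfect device with independent control error; for an imperfect one, step 3 shows the reverse is possible.
- **The unit is not stated.** H.vi speaks of crossing an alarm threshold, and alarms are logged separately, so the unit could be the reading, the alarm or the woman. One reading per time point is inferred from the form, and the percentages above apply only to paired readings.

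It is also tempting to treat the control's agreement with its own next reading as the least an equally good device should reach. Step 4 shows that this fails. Real change between readings lowers that agreement, as does any treatment prompted by a high reading, since clinical decisions follow the control. Sharing one device, cuff and arm raises it, whereas Sphygmo sits on the other arm.

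**Conclusion.** The concern holds as a matter of what the results measure. Under H.vi's scoring, they are agreement with the control and not accuracy against true pressure. With roughly independent errors, even a perfect Sphygmo falls short of 100% on both measures, and the shortfall in sensitivity is greatest at the severe cut-off when few readings lie above it. In the tabulated cases that sensitivity is about 65–94%, and the wider grid reaches lower. These figures are illustrations that rest on assumed error SDs, pressure distributions and cut-offs. Only the mechanism follows from the documents.

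The documents do not support saying that reported sensitivity must be too low, by how much it would be off, or that an unwarranted redesign would follow; the Executive Summary ties design changes to performance, use and usability together. The change is worth making because it affects how the key results may be interpreted and reused, at almost no cost.

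**What to change.** 1. In H.vi and the Executive Summary, report the two results as positive and negative percent agreement with the control. State that they are not to be carried into full-trial planning as true sensitivity and specificity.
2. From the paired readings already on the form, add the mean and SD of the Sphygmo-minus-control difference, allowing for repeated readings per woman. The difference contains both monitors' error and any between-arm difference, so it should not be attributed to Sphygmo alone.
3. Show how far discordant pairs lie from the cut-off, so that near-threshold disagreement can be told from large disagreement. This needs the programmed thresholds on record for each woman.
4. Give intervals that resample women, not readings. With at most 20 women they will be rough.
5. Control-versus-next-control agreement may be shown as descriptive context only, with a note that it is not a lower bound and can err in either direction.

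The cost is some wording and a little more analysis, with no new data or procedures. The downside is a less favourable label for the key results.

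### Sensitivity and specificity are to have confidence intervals, but the counting unit and interval method are not stated and nothing allows for repeated readings within a woman

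*Combined protocol and SAP*

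**What the plan says.** The Threshold Accuracy list in section H.vi builds a two-by-two table from agreement between the devices, for example "True positive (TP): Control device and Sphygmo cross alarm threshold". From it come "Sensitivity: TP/(TP+FN) with confidence intervals" and "Specificity: TN/(TN+FP) with confidence intervals". No counting unit, confidence level or interval method is given. The usability and device-function items in the same section do have a unit: user error is capped at one per device interaction and malfunction at one per device use.

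Three places bear on the unit:
- The primary efficacy objective (section G) is to "Determine whether the Sphygmo device correctly identifies instances where systolic and diastolic blood pressures meet the diagnostic criteria".
- The Executive Summary says "Blood pressure measurements by Sphygmo and the commercial device will continue until monitoring is no longer clinically prescribed", so each woman gives several readings.
- The Blood Pressure Measurements form pairs one control and one test-device reading in each numbered row.

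The forms also include a separate alarm log with time, device and alarm type.

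The Executive Summary names as key results the "sensitivity and specificity of the Sphygmo device for identifying blood pressure levels corresponding to mild and severe pre-eclampsia". Section H.vi, however, defines one table on one alarm threshold. Section H.vii names Excel and Matlab and lists descriptive summaries. Neither it nor the sample-size section (H.v) mentions correlation within a woman.

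**The concern.** A confidence interval for a proportion depends on what is counted and on whether the counts are independent. If paired readings from about 20 women are pooled and given an ordinary binomial interval, every reading is treated as if it came from a different woman. That is doubtful here. The Executive Summary puts Sphygmo on one arm and the commercial cuff on the other, so a between-arm difference or a poor cuff fit would tend to recur through a woman's readings. With positive correlation the interval is too narrow, and the pilot would appear to have measured its key results more precisely than it did.

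Section H.v also says the pilot is meant to supply the data for sizing a full trial. Should that trial use a reading-level endpoint and be sized as if readings were independent, it would enrol too few women.

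**Working it through.** **Inputs from the documents.** 20 women, raised from 10 to allow for withdrawals (H.v). No expected sensitivity, target width, confidence level or planned readings per woman is stated, so there is no precision figure to reproduce.

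**Assumed inputs.** True sensitivity 90%; m control-positive readings per woman, equal across women; ICC from 0 to 0.2; 95% level.

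**Design effect.** DE = 1 + (m − 1) × ICC. The effective number of readings is 20m/DE, and the correct interval is wider by √DE. With m = 10 there are 200 readings, and the naive half-width is 1.96 × √(0.9 × 0.1/200) = 0.042.
- ICC 0.1: DE = 1 + 9 × 0.1 = 1.9; effective number 200/1.9 = 105; half-width 0.042 × √1.9 = 0.057.
- ICC 0.2: DE = 1 + 9 × 0.2 = 2.8; effective number 200/2.8 = 71; half-width 0.042 × √2.8 = 0.070.

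**Coverage of nominal 95% intervals.** Beta-binomial simulation, 20,000 runs per setting. Repeat runs agree to within about half a point.

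| Women | m | ICC | Pooled exact | Clustered on woman |
|---|---|---|---|---|
| 20 | 10 | 0 | 96.5% | 95.6% |
| 20 | 5 | 0.05 | 93.3% | 96.3% |
| 20 | 10 | 0.1 | 87.9% | 95.4% |
| 20 | 10 | 0.2 | 79.6% | 94.5% |
| 10 | 10 | 0.1 | 85.6% | 94.5% |

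The clustered interval uses a cluster-robust variance on the logit scale with a K/(K − 1) correction and t on K − 1 degrees of freedom, where K is the number of women.

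**An illustration without an assumed ICC.** Suppose 20 false negatives in 200 control-positive readings (20 women × 10), so the estimate is 90%. The pooled exact interval is 85.0% to 93.8% however the errors are spread. For the clustered interval, each woman's residual is her false negatives minus the expected 1.
- Ten women with 2 each: sum of squared residuals 10 × 1² + 10 × 1² = 20. SE = √((20/19) × 20)/200 = 0.0229; on the logit scale 0.0229/0.09 = 0.255. With t = 2.093 on 19 degrees of freedom, the interval is 84.1% to 93.9%, close to the pooled one.
- Five women with 4 each: sum of squares 5 × 3² + 15 × 1² = 60. SE = √((20/19) × 60)/200 = 0.0397; logit SE 0.442. The interval is 78.1% to 95.8%.

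**Limits of the clustered interval.** It rests on how errors vary between women, so it needs several women with a discordant reading. Share of runs with fewer than five such women (m = 10, ICC 0.1):

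| True sensitivity | 20 women | 10 women |
|---|---|---|
| 90% | 0.4% | about 33% |
| 95% | 24% | 85% |
| 98% | 89% | 99% |

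Its coverage also slips in harder cases: 92% with uneven readings (mean 10, ICC 0.2, sensitivity 90%) and 90.5% with m = 15, ICC 0.3 and sensitivity 95%.

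**Effect on a later reading-level trial.** For ±5 points at sensitivity 90%, independent readings needed = 1.96² × 0.9 × 0.1/0.05² = 138.3. Women needed = 138.3 × DE/10, rounded up: 14 if readings are independent, and 21, 27 and 39 at ICC 0.05, 0.1 and 0.2.

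**The case against.** The plan is silent rather than wrong: it promises confidence intervals and names software, and it may be that a suitable method would be used. The unit is open too. Because the table is defined by crossing an alarm threshold and a separate alarm log is kept, an alarm episode is a possible unit. Section H.v speaks of numbers of patients and of diagnosing pre-eclampsia, which could suggest the woman. If each woman were counted once, within-woman correlation would not arise. The study is a small descriptive pilot, and the recommended interval is itself weak with 10 women.

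Most of this stands, and it limits the point to an omission whose size is unknown. It does not remove the omission. Paired readings remain the most natural unit given the objective, the repeated measurement and the form, and alarm episodes would also recur within a woman.

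Three stronger readings are tempting and not supported:
- A reader might infer that the plan specifies ordinary binomial intervals. It names no method.
- A reader might take the form's 45 rows as 45 readings per woman, for which pooled exact coverage falls to about 61% at ICC 0.1 with 20 women. The rows are room on the form, not a planned count, and sensitivity uses only control-positive readings.
- A reader might infer that the full trial will be too small. That needs a reading-level endpoint and sizing as if readings were independent; the documents state neither.

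**Conclusion.** The point holds as a conditional one and should be fixed before analysis. For its key results the plan gives neither the counting unit nor the interval method, and it makes no provision for repeated readings within a woman. If readings are pooled and positively correlated, ordinary binomial intervals overstate precision. Under the assumed inputs the shortfall in coverage runs from about 2 points (5 readings, ICC 0.05) to about 15 points (10 readings, ICC 0.2). The documents do not show which case applies, because they give neither the ICC nor the number of readings per woman. Point estimates and data capture are unaffected. This rests on the visible text only, since many passages were removed before review.

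**What to change.** In sections H.vi and H.vii:
1. State the counting unit. A sensible default is the time-matched paired reading, one row of the form. Give separate two-by-two tables for the mild and the severe level, as the Executive Summary implies.
2. Keep the pooled estimates, but compute each 95% interval clustered on woman: cluster-robust variance on the logit scale, with t on the number of contributing women minus 1 degrees of freedom.
3. Report readings per woman and, for each measure, the number of women contributing and the number with a discordant reading. Where few women are discordant, say that the clustered interval is unreliable (not estimable with none), and label any exact interval on readings as assuming independence.
4. If the later trial uses a reading-level endpoint, size it over a range of ICC values.

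This changes analysis wording only; the form already records paired readings for each patient. The costs are wider reported intervals, and clustered intervals that will often be unreliable with about 10 women or very high sensitivity. What counts as few discordant women is a judgement and should be set in advance.
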